Exploratory endpoints will be compared analogously, with the exception of a prespecified alpha-controlling testing strategy. *P*-values for exploratory endpoints will be considered descriptive and not considered conclusive.

The primary efficacy analyses will use the treatment policy estimands, using all available data from all randomized subjects regardless of treatment compliance. Subjects will be analyzed in the group to which they are randomized. Subjects who do not have an evaluation for a dichotomous endpoint at a given timepoint will be imputed as nonresponders. Subjects who do not have a continuous measure at a given timepoint will have available data at other timepoints included in the longitudinal model, resulting in an analysis that is robust to data that are missing at random or missing completely at random. Sensitivity and supplementary analyses will be used to assess the impact of missing data assumptions.

Incidence of TEAEs over the first 16 weeks will be summarized by randomized treatment group. No *p*-values will be reported. Incidence will also be summarized over all 52 weeks for subjects randomized to receive izokibep, and summarized over the last 36 weeks for subjects randomized to receive placebo for the first 16 weeks. Serious adverse events will be summarized analogously. Subjects will be summarized for safety according to treatment actually received.

[figure not shown]
Available PK data will be summarized by dose group of izokibep.

Incidence of ADAs at any time will be summarized by treatment group and overall.

At Week 16 response rates for ACR50 are expected to be 20% for placebo and 45% for a dose regimen of 160 mg izokibep (QW or Q2W or both). With 100 subjects receiving placebo and 100 subjects receiving a dose regimen of izokibep, there will be 97% power to show a difference in the primary endpoint of ACR50 response rate. If a 45% response rate is observed with a dose regimen of izokibep, the 2-sided 95% confidence interval for the true response rate will have a half-width of approximately 10 percentage points.

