7.1. Discontinuation of Study Drug

In rare instances, it may be necessary for a subject to permanently discontinue study drug. The reason for permanent discontinuation of study drug will be documented. If study drug is prematurely and permanently discontinued, the subject will be encouraged to remain in the study to be evaluated for safety and efficacy. Subjects should continue to complete study assessments as outlined in the SoA ([Section 1.3](#)) where possible, with the exception of study drug administration, and anti-drug antibody sample and PK sample collection. Reasons for removal from study drug include any of the following:

- subject request
- death
- lost to follow-up
- termination of study by sponsor
- emergency unblinding
- liver chemistry stopping criteria (see [Section 7.1.1](#))
- serious infections
- the subject becomes pregnant while on study drug
- malignancy
- subject develops CTCAE v5.0 grade 3 or higher SAE or AE(s) that is considered by the investigator to be related to study drug
- subject develops an illness that, in the opinion of the Investigator, would interfere with his or her continued participation, if the risk of continuing with study drug outweighs the potential benefit
- subject uses prohibited concomitant medications, as defined in [Section 6.8.3](#), that may present a risk to the safety of the subject in the opinion of the Investigator or the Medical Monitor
- subject is non-compliant with TB prophylaxis (if applicable) or develops active TB at any time during the study
- subject is significantly non-compliant with study procedures which would put the subject at risk for continued participation in the trial as determined by the Investigator or Medical Monitor
- subjects with disease progression or not responding to treatment are to be withdrawn from study drug treatment based on Investigator's discretion

- Starting at Week 24, subjects who have not met clinical Disease Activity for PsA (cDAPSA) low disease activity ($cDAPSA \leq 14$) at 2 consecutive visits (e.g. at Week 20 and Week 24) will be discontinued from study drug and can receive standard of care treatment as deemed appropriate by the Investigator.

Subjects with newly diagnosed IBD during the study must:

- discontinue study drug and be followed-up until resolution of active IBD symptoms
- be referred, as appropriate, to a health care professional treating IBD, such as a gastroenterologist

[figure not shown]

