## 2. Protocol Details

### 2.1. Overall Study Design

This is a multicenter, randomized, double-blind, placebo-controlled, Phase 2b/3 Study to evaluate the clinical question of the effects of the efficacy and safety of izokibep in subjects with active psoriatic arthritis (PsA) who are tumor necrosis factor-alpha inhibitor (TNFi) naïve, who have had an inadequate response or intolerance to TNFi, or for whom TNFi is contraindicated. Approximately 325 subjects with active PsA will be enrolled. The study consists of up to a 28-day (4-week) screening period, a 51-week treatment period, and a follow-up period with visits at 8 weeks and 14 weeks after the last dose of study drug to assess safety and immunogenicity.

Subjects meeting eligibility criteria will be randomized into 1 of 4 treatment groups in a 4:4:4:1 ratio as follows:

- Group 1 (n=100): placebo every week (QW) from Day 1/Week 0 to Week 15, then izokibep 160 mg QW from Week 16 to Week 51.
- Group 2 (n=100): izokibep 160 mg QW from Day 1/Week 0 to Week 51.
- Group 3 (n=100): izokibep 160 mg every 2 weeks (Q2W) from Day 1/Week 0 to Week 50, with matching placebo Q2W until Week 51 for the weeks in between izokibep doses to maintain the blind.
- Group 4 (n=25): izokibep 80 mg every 4 weeks (Q4W) from Day 1/Week 0 to Week 48, with matching placebo QW until Week 51 for the weeks in between izokibep doses to maintain the blind.

Randomization will be stratified by prior TNFi use (Yes/No) and enthesitis (Leeds Enthesitis Index [LEI] > 0/LEI = 0). Anticipated enrollment of subjects previously treated with TNFi is 20% to 30%. The number of subjects without enthesitis entering into the study (LEI = 0 at baseline) will be capped at 70%.

Subjects will complete study assessments according to the study visits outlined in the Schedule of Activities (SoA) in the protocol. The primary endpoint will be assessed at Week 16. The last dose of study drug will be administered on Week 51.

Starting at Week 24, subjects who do not meet clinical Disease Activity for PsA (cDAPSA) low disease activity (cDAPSA  $\leq$ 14) at 2 consecutive visits (e.g. at Week 20 and Week 24) will be discontinued from study drug and can receive standard of care as deemed appropriate by the investigator.

An End of Treatment (EOT) visit will be conducted at Week 52. A Safety Follow-up visit will be conducted at Week 59. A pharmacokinetic/anti-drug antibody (PK/ADA) Follow-up and

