## 6.7. Safety

For all Safety Tables, data will be summarized as follows, unless otherwise specified:

- Period 1 will include the first 16 weeks, summarized by the randomized treatment arms (Placebo QW; Izokibep QW; Izokibep Q2W, Izokibep Q4W)
- Period 2 will include data after Week 16 visit, summarized by the randomized treatment groups (Placebo - Izokibep QW; Izokibep QW; Izokibep Q2W, Izokibep Q4W)
  - Selected AE summaries will be presented as: Period 2 will include data after Week 16 visit, summarized by Placebo - Izokibep QW; Izokibep QW (those who receive QW during any part of period 2); Izokibep Q2W (those who receive Q2W during any part of period 2); Izokibep Q4W (those who receive Q4W during any part of period 2); Izokibep QW only (those who receive only izokibep QW during period 2); Izokibep Q2W only (those who receive only izokibep Q2W during period 2); Izokibep Q4W only (those who receive only izokibep Q4W during period 2)

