### 6.7.2. Adverse Events

All SAEs will be collected from the signing of the ICF until the 8-week follow-up visit. All AEs will be collected from the first dose of study drug until 4 weeks after the last dose of study drug. All AEs recorded on the eCRF will be coded using the latest MedDRA dictionary around the time of Database Lock and classified as either AEs or treatment-emergent AEs (TEAEs) as follows:

- TEAEs are either events with start date and time after the start of the Treatment Period and up to 4 weeks after the end of the Treatment Period, or events with start date and time prior to the start of the Treatment Period whose severity worsens on or after the start of the Treatment Period. TEAEs for period 2 are either events with start date and time after the start of administration of Week 16 treatment and up to 4 weeks after the end of the Treatment Period, or events with start date and time prior to the start of administration of Week 16 treatment whose severity worsens on or after the start of administration of Week 16 treatment. For subjects who receive treatment in period 2, TEAEs with start date after the start of period 2 will be assigned to period 2 only, not to period 1.
- Treatment-Emergent Serious AEs (TESAEs) will be defined as TEAEs which meet the criteria as Serious = “Yes”.
- The relationship between a TEAE and treatment is assessed as related or not related. A treatment-related TEAE will be defined as a TEAE considered by the investigator as related to treatment or with unknown/missing relationship to treatment.
- Assessment of AE severity will be based on eCRF AEs form.
- TEAEs leading to discontinuation of treatment are defined as TEAEs where “Action Taken with Study Treatment” is indicated as “Drug Withdrawn”.

In addition to the aforementioned AE types, the following TEAEs of special interest will be monitored:

- Candida infection,
- Inflammatory bowel disease,
- Suicidal ideation.
- Malignancies
- MACE (major adverse cardiovascular and cerebrovascular events: cerebrovascular accident and transient ischemic attack, non-fatal myocardial infarction or unstable angina, cardiovascular death)
- Tuberculosis (TB)
- Infections (serious, opportunistic, or fungal only)
- Cytopenias

- Systemic hypersensitivity reaction

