Adverse events of special interest will be identified manually. After all data are entered into the database and before database unblinding, a list of all unique PTs will be generated. ACELYRIN pharmacovigilance and clinical development representatives will review the list and determine which are TEAEs of special interest in each category listed above. This determination will be documented in a memo, signed and dated before database lock, and stored in the study trial master file. The database will not be unblinded until the memo is finalized and signed.

Adverse events will be summarized by default descriptive summary statistics for categorical variables for the Safety Analysis Set as follows:

- An overview of TEAEs including the number and percentage of subjects with at least one of each mentioned TEAE type according to both Period 2 groupings as described in section 6.7:
  - Any TEAE
    - Leading to discontinuation of study treatment
    - Mild (Grade 1)
    - Moderate (Grade 2)
    - Severe (Grade 3)
    - Life-threatening (Grade 4)
    - Death (Grade 5)
    - Any TEAE
      - Grade 2 or higher
      - Grade 3 or higher
      - Grade 4 or higher
  - Any study treatment related TEAE
    - Leading to discontinuation of study treatment
  - Any serious TEAE
    - Leading to discontinuation of study treatment
    - Leading to death
  - Any serious study treatment related TEAE
    - Leading to discontinuation of study treatment
    - Leading to death
- The number and percentage of subjects reporting each TEAE and the count of number of events will be summarized by SOC and PT for the following types of TEAEs.
  - TEAEs
  - TEAEs of Special Interest
  - TEAEs Leading to Discontinuation of Study Treatment

- TEAEs leading to interruption of study treatment
- TEAEs by Maximum Severity
- TEAEs by Relationship to Treatment
- TEAEs by Relationship and Maximum Severity
- Study Treatment related TEAEs
- Study Treatment Related TEAEs Leading to Discontinuation of Study Treatment
- Serious TEAEs
- Serious TEAEs Leading to Discontinuation of Study Treatment
- Serious TEAEs Leading to Death
- Study Treatment Related Serious TEAEs
- Study Treatment Related Serious TEAEs Leading to Discontinuation of Study Treatment
- Study Treatment Related Serious TEAEs Leading to Death
- The number and percentage of subjects reporting each TEAE and the count of number of events will be summarized by SOC and PT for two subgroups:
  - Subjects < 65 years of age at baseline

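### Period 2 adverse events are planned as crude percentages although an efficacy-based stop from Week 24 shortens follow-up unequally, and the Weeks 0-52 incidence in the protocol has no specified table

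*SAP*

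**What the plan says.** **Tables.** SAP 6.7 makes Period 1 the first 16 weeks, and "Period 2 will include data after Week 16 visit, summarized by the randomized treatment groups". SAP 6.7.2 gives the statistic: "The number and percentage of subjects reporting each TEAE and the count of number of events will be summarized by SOC and PT". Under SAP 6.1 the denominator is the number of subjects in the analysis population, unless the table shells say otherwise. No person-time rate or time-to-event estimate is named for AEs. Events that start in Period 2 are assigned to Period 2 only.

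**Stop.** From Week 24, subjects who miss cDAPSA low disease activity "at 2 consecutive visits (e.g. at Week 20 and Week 24) will be discontinued from study drug" (SAP 2.1). Protocol 7.1 has the same rule.

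**Collection.** SAP 6.7.2: "All AEs will be collected from the first dose of study drug until 4 weeks after the last dose of study drug", and "All SAEs will be collected from the signing of the ICF until the 8-week follow-up visit". SAP 2.1: "The last dose of study drug will be administered on Week 51".

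**Treatment-emergent window.** SAP 6.7.2 runs it to 4 weeks after the end of the Treatment Period, not after the last dose. SAP 5.1.3 ends that period at Week 52 or at early termination, where the end-of-treatment visit falls within 14 days of withdrawal. Serious TEAEs are the serious subset of TEAEs.

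**Whole study.** Protocol 1.1: "Incidence will also be summarized over all 52 weeks for subjects randomized to receive izokibep". Protocol 9.3.5 asks for AE summaries in the primary phase and overall. SAP 6.7.7 keeps a general commitment to summarize all safety data through study end, but gives no table, window or grouping. SAP 6.7.2 lists no Weeks 0-52 AE table.

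**The concern.** A crude percentage compares groups fairly only if their subjects are followed for similar lengths of time. Here follow-up depends on response to treatment, so a group with more cDAPSA failures accrues less time in which an AE can be recorded. The documents give reasons to expect unequal stopping. Protocol 4.3 predicts higher responses for the 160 mg regimens than for 40 mg and 80 mg Q2W, and the study includes a lower 80 mg Q4W arm. The placebo-to-QW group has had only 4 and 8 weeks of active drug at the Week 20 and Week 24 checks. All four groups stand side by side in the Period 2 tables.

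Safety is a secondary objective, and Period 2 holds most of the long-term data, including events of special interest. Without a single Weeks 0-52 count, a reader also cannot say what fraction of subjects on a regimen had a given event over the planned year.

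**Working it through.** The plan states no figure for this point, so there is none to reproduce.

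**1. AE follow-up from Week 16**

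- Completer: last dose Week 51, so 51 + 4 − 16 = 39 weeks.
- Stopped at Week 24: last dose Week 23 gives 23 + 4 − 16 = 11 weeks; last dose Week 24 gives 12. That is 28% to 31% of the completer's window.
- Stopped at the Week 32 visit: last dose Week 31 gives 31 + 4 − 16 = 19 weeks.
- SAE collection runs to 8 weeks: 51 + 8 − 16 = 43 weeks against 24 + 8 − 16 = 16 weeks (37%).

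**2. Crude percentage at equal hazard**

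The documents give neither stop shares nor AE rates, so both are assumptions. Take a constant rate r per person-year, the same in both groups, and a share s stopped at Week 24:

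P(w) = 1 − exp(−r × w/52)

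Crude % = (1 − s) × P(39) + s × P(11)

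| r | P(39) | P(11) | 20% stopped | 40% stopped | Gap (points) |
|---|---|---|---|---|---|
| 0.5 | 31.3% | 10.0% | 27.0% | 22.8% | 4.2 |
| 1 | 52.8% | 19.1% | 46.0% | 39.3% | 6.7 |
| 2 | 77.7% | 34.5% | 69.0% | 60.4% | 8.6 |

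The gap equals (s2 − s1) × (P(39) − P(11)). At r = 1:

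- 20% versus 30% stopped: 0.1 × (52.8 − 19.1) = 3.4 points. Equal shares give zero.
- 20% versus 40%, all stops at the Week 32 visit: P(19) = 30.6%, so 0.2 × (52.8 − 30.6) = 4.4 points.

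**3. Exposure-adjusted rate**

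Under this model the expected time to first event or end of follow-up is P(w)/r for each subject. Expected first events divided by expected person-time is therefore r, whatever s is. At r = 1 both groups show 100 first events per 100 person-years.

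**4. Sensitivity of size and direction**

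This step uses 12 weeks for stopped subjects and shares of 20% versus 50%.

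- With a 39-week risk of 10%, 30% or 50%, equal hazards give 8.6% vs 6.6%, 26.1% vs 20.2%, and 43.8% vs 34.6%. The apparent risk ratios are 0.76 to 0.79.
- A true hazard ratio of about 1.33 to 1.39 against the group with more stops would be hidden.
- At the 30% setting, if stopped subjects have 3 times the hazard the groups nearly agree (29.6% vs 29.0%). At 4 times the order reverses (31.1% vs 32.8%).

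**5. Weeks 0-52**

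Period percentages cannot be combined. If 30% of subjects have an event in each period, the 52-week figure can be anything from 30% (the same subjects) to 60% (different subjects).

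**The case against.** The randomized placebo comparison is in Period 1, which the Week 24 rule cannot touch. Period 2 is descriptive, no safety p-values are planned, and the secondary objective is worded as incidence, which the SAP does report. The SAP also supplies partial remedies: Period 2 dose counts by group (SAP 6.5), event counts, the number of subjects missing the cDAPSA criterion by group (SAP 6.2), exposure through the primary endpoint and for the entire study (SAP 6.7.1), and listings with dates. Every group is dosed weekly, so dose counts approximate weeks on drug. Exposure-adjusted rates have their own limits: they assume a roughly constant hazard and do not correct for who stays on drug.

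Much of this stands and limits the weight of the point. It does not remove it. Dose counts and event counts allow a rough event rate, but not a first-event rate that includes the post-dose tail, and exposure duration is not given for Period 2 on its own. For compliance, SAP 6.5 already adjusts the expected Period 2 doses for subjects withdrawn under the Week 24 rule; the AE tables make no matching allowance.

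Two stronger readings are tempting. A reader might infer that the less effective regimen will look safer. That needs unequal stop shares and similar hazards in stopped and continuing subjects, and the documents give neither. The sample-size sections do not rank QW and Q2W. A reader might also infer that the 52-week incidence was dropped. SAP 6.7.7 keeps a whole-study summary, the period split in SAP 6.7 applies unless otherwise specified, and the table shells are not among the documents. The incidence is unspecified, not withdrawn.

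**Conclusion.** The point holds in a limited form. Period 2 crude percentages are not comparable between groups whose stop shares differ, and at equal hazard the group with more stops can look safer. Follow-up is about 39 weeks for a completer against 11 to 12 for a Week 24 stop, and longer for later stops. At 1 event per person-year with all stops at Week 24, the artefact is 6.7 points for 20% versus 40% stopped and 3.4 points for 20% versus 30%. It is smaller if stops come later, absent if shares are equal, and can reverse if stopped subjects have a much higher hazard. Shares and rates are assumptions throughout.

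The 4-week limit applies to AE collection. SAEs are collected for longer, but the serious-TEAE tables are still cut at the treatment-emergent window, which matches neither collection window. Separately, the Weeks 0-52 incidence for izokibep-randomized subjects needs a specified table.

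**What to change.** In SAP 6.7.2:

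1. Add exposure-adjusted incidence (subjects with a first event per 100 person-years at risk) to the Period 2 TEAE, serious TEAE and special-interest tables. End time at risk at the first event or at the end of the SAP's own treatment-emergent window.
2. Align that window with the AE and SAE collection windows, so that the events counted and the time at risk cover the same interval.
3. Specify a Weeks 0-52 TEAE and serious TEAE table for the izokibep-randomized arms, with each subject counted once.

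Keep the crude percentages alongside. The cost is extra table columns and one table set, with no new data and no alpha. The rate's constant-hazard assumption, and the fact that it leaves selection of who stays on drug in place, should be footnoted. The stopping rule is unchanged.

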### 6.7.1. Extent of Exposure

Exposure will be reported through the planned collection of the primary endpoint and for the entire study for the Safety Analysis Set. Exposure duration will also be summarized and will be calculated as (last dose – first dose + 1). Descriptive statistics will be presented for duration of exposure.

A listing of overall treatment exposure data, including the first and last dates of treatment will be presented together with compliance for the Safety Analysis Set. Further, study treatment administration data will be listed for the Safety Analysis Set.

### 6.7.2. Adverse Events

All SAEs will be collected from the signing of the ICF until the 8-week follow-up visit. All AEs will be collected from the first dose of study drug until 4 weeks after the last dose of study drug. All AEs recorded on the eCRF will be coded using the latest MedDRA dictionary around the time of Database Lock and classified as either AEs or treatment-emergent AEs (TEAEs) as follows:

- TEAEs are either events with start date and time after the start of the Treatment Period and up to 4 weeks after the end of the Treatment Period, or events with start date and time prior to the start of the Treatment Period whose severity worsens on or after the start of the Treatment Period. TEAEs for period 2 are either events with start date and time after the start of administration of Week 16 treatment and up to 4 weeks after the end of the Treatment Period, or events with start date and time prior to the start of administration of Week 16 treatment whose severity worsens on or after the start of administration of Week 16 treatment. For subjects who receive treatment in period 2, TEAEs with start date after the start of period 2 will be assigned to period 2 only, not to period 1.
- Treatment-Emergent Serious AEs (TESAEs) will be defined as TEAEs which meet the criteria as Serious = “Yes”.
- The relationship between a TEAE and treatment is assessed as related or not related. A treatment-related TEAE will be defined as a TEAE considered by the investigator as related to treatment or with unknown/missing relationship to treatment.
- Assessment of AE severity will be based on eCRF AEs form.
- TEAEs leading to discontinuation of treatment are defined as TEAEs where “Action Taken with Study Treatment” is indicated as “Drug Withdrawn”.

In addition to the aforementioned AE types, the following TEAEs of special interest will be monitored:

- Candida infection,
- Inflammatory bowel disease,
- Suicidal ideation.
- Malignancies
- MACE (major adverse cardiovascular and cerebrovascular events: cerebrovascular accident and transient ischemic attack, non-fatal myocardial infarction or unstable angina, cardiovascular death)
- Tuberculosis (TB)
- Infections (serious, opportunistic, or fungal only)
- Cytopenias

- Systemic hypersensitivity reaction

Adverse events of special interest will be identified manually. After all data are entered into the database and before database unblinding, a list of all unique PTs will be generated. ACELYRIN pharmacovigilance and clinical development representatives will review the list and determine which are TEAEs of special interest in each category listed above. This determination will be documented in a memo, signed and dated before database lock, and stored in the study trial master file. The database will not be unblinded until the memo is finalized and signed.

Adverse events will be summarized by default descriptive summary statistics for categorical variables for the Safety Analysis Set as follows:

- An overview of TEAEs including the number and percentage of subjects with at least one of each mentioned TEAE type according to both Period 2 groupings as described in section 6.7:
  - Any TEAE
    - Leading to discontinuation of study treatment
    - Mild (Grade 1)
    - Moderate (Grade 2)
    - Severe (Grade 3)
    - Life-threatening (Grade 4)
    - Death (Grade 5)
    - Any TEAE
      - Grade 2 or higher
      - Grade 3 or higher
      - Grade 4 or higher
  - Any study treatment related TEAE
    - Leading to discontinuation of study treatment
  - Any serious TEAE
    - Leading to discontinuation of study treatment
    - Leading to death
  - Any serious study treatment related TEAE
    - Leading to discontinuation of study treatment
    - Leading to death
- The number and percentage of subjects reporting each TEAE and the count of number of events will be summarized by SOC and PT for the following types of TEAEs.
  - TEAEs
  - TEAEs of Special Interest
  - TEAEs Leading to Discontinuation of Study Treatment

- TEAEs leading to interruption of study treatment
- TEAEs by Maximum Severity
- TEAEs by Relationship to Treatment
- TEAEs by Relationship and Maximum Severity
- Study Treatment related TEAEs
- Study Treatment Related TEAEs Leading to Discontinuation of Study Treatment
- Serious TEAEs
- Serious TEAEs Leading to Discontinuation of Study Treatment
- Serious TEAEs Leading to Death
- Study Treatment Related Serious TEAEs
- Study Treatment Related Serious TEAEs Leading to Discontinuation of Study Treatment
- Study Treatment Related Serious TEAEs Leading to Death
- The number and percentage of subjects reporting each TEAE and the count of number of events will be summarized by SOC and PT for two subgroups:
  - Subjects < 65 years of age at baseline
  - Subjects  $\geq$  65 years of age at baseline
- The number and percentage of subjects who died will be summarized
- The number and percentage of subjects reporting each TEAE and the number of events will be summarized by PT for all TEAEs
- The number and percentage of subjects reporting each TEAE and the number of events will be summarized by PT for TEAEs of Special Interest
- The number and percentage of subjects reporting each TEAE and the count of number of events according to the 5 Period 2 groupings as described in section 6.7 will be summarized by SOC and PT for the following types of TEAEs.
  - All TEAEs
  - Serious TEAEs

In the above summaries, subjects with more than one TEAE within a particular SOC are counted only once for that SOC. Similarly, subjects with more than one TEAE within a particular PT are counted only once for that PT.

For summaries by maximum severity, subjects with multiple TEAEs within a particular SOC or PT will be counted under the category of their most severe TEAE within that SOC or PT. TEAEs with missing severity will be included in the counts as severe (Grade 3) unless the TEAE has an outcome of fatal; in that case, the TEAE with missing severity will be included in the counts as death (Grade 5).

Summaries by SOCs and PTs will be sorted by SOCs by their Internationally Agreed Order (MedDRA) and PTs within SOC by descending order of total incidence. Where PTs tie, PTs will be sorted alphabetically.

All AE data will be listed and AEs and TEAEs will be presented together. Treatment-emergence status will be flagged in the listing. The listing will present the relative start and stop day of the AE calculated relative to the first dose of treatment and will be presented for those subjects who received at least one dose of treatment. If the AE is “Ongoing” it will be indicated as such in the listing and the relative stop day will not be calculated. Only original dates will be presented in the listing even though the relative day may be based on an imputed date.

In addition, the following listings will be presented:

- Listing of Deaths
- Listing of TEAEs
- Listing of Serious TEAEs
- Listing of AEs Leading to Interruption of Study Treatment
- Listing of AEs Leading to Discontinuation of Study Treatment
- Listing of AEs of Special Interest

